#### 8.2 JUSTIFICATION OF SAMPLE SIZE

The calculated sample size for the study is based on conservative imputation of results from other studies on weight loss including the use of TENS for weight loss. The degree of coaching/dietary support throughout the present study is moderate intensity lifestyle/weight coaching. The sample size modeling assumes an average of 3.5% TBWL in Control subjects using diet and exercise alone. The estimated weight loss in the Treatment subjects is modeled from preliminary data on T6/T7 dermatomal TENS when used for weight loss: 7.5% TBWL. The variance of the responses in the study (i.e. Standard Deviation) was modeled at + 5% TBWL. This value was taken from previous dermatomal TENS weight loss study results. The model assumes a 30% drop out rate across groups and an 80% powered endpoint using an adaptive p spending model wherein interim posterior probability assessments are allowed after enrolling proscribe cohorts of not less than 25 subjects per group for not less than 7 weeks of stimulation. The alpha penalty will be minimized per interim by assessing the relationship between stimulation (i.e. dose) and weight loss using Normalized Linear Dynamic Modeling (NLDM) to determine overall sample size projected (i.e. futility) rather than assessing the primary endpoint hypothesis per se. Monotonicity will not be assumed in this analysis. This modeling provides an estimate of 75 subjects per group, for a total study size of 150 subjects. However, the protocol allows for enrollment of additional subjects should the interim model project under powering of the primary endpoint.

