	At the end of the Therapy Period, subjects will complete an end of study visit to be assessed for weight loss, blood pressure, blood lipids, hemoglobin A1c, CMP (Reduction of ALT), patient preference questionnaire and their participation will be considered complete (pending laboratory results, adverse events or serious adverse events).
	The study utilizes an adaptive approach where cohorts of enrolled/randomized subjects (in groups of 25 per arm) are assessed for dose response and progression to achievement of primary and secondary endpoints. Frequent interim endpoint

	assessment utilizing Markov-chain Monte Carlo (MCMC) methods coupled with Longitudinal analyses will be utilized to determine sample sizes for future cohorts (assessed primarily via Normal dynamic linear modeling [NDLM]).
Subject Population / Sample Size	The primary endpoint is powered at a final enrollment of 75 subjects per group, for a total of 150 subjects, but interim analyses based on Bayesian posterior probability distributions with multiple imputation will be utilized to assess interim significance.
	In the event the interim analysis is not significant, up to 300 subjects may need to be enrolled in order to achieve final separation between groups for statistical significance. Thus, Elira may need to screen up to 500 subjects to account for exclusions prior to enrollment.
Study Duration and Sites	Minimum study duration for each patient will be 13 weeks. As it is expected that recruitment of 150 subjects will take up to 12 weeks, the overall study duration is anticipated to be a minimum of 26 weeks, assuming all cohorts are enrolled. The study will be conducted at up to 10 centers.
Inclusion	Subject is between 18 – 65 years of age inclusive.
Criteria	Subject has a BMI of 25-35 kg/ m² inclusive.
	Subject has signed the informed consent form and is able to comply with study protocol and adhere to study visit schedule.
	Subject is able to wear and use a wearable, patch TENS system.
	Subject is able to use a touch screen hand held smart phone.
	Subject is fluent in English and can complete patient questionnaires.
	Subject can comply with a 1200 calorie diet for the duration of the study.
	Subject is male or non-pregnant, non-lactating female, who agrees to use effective contraceptive methods throughout the length of the trial based on PI approval.

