#### 6.1.2 Primary Effectiveness Endpoint:

The primary effectiveness endpoint is the percent reduction in total body weight loss (%TBWL), measured as End Weight – Initial Weight divided by Initial Weight, multiplied by 100, at the end of Therapy period compared to Baseline between Treatment and Control.

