#### 8.1.3 Weight Loss

The null and alternative hypotheses are:

$$H_0$$
:  $π_T ≤ π_C$ 
 $H_1$ :  $π_T > π_C$ 

Where  $\pi_T$  and  $\pi_C$  are the probabilities of weight loss (% TBWL, %EBWL) in treatment versus control respectively. Estimates of the proportion of weight loss in pounds, % total body weight loss (%TBWL) Excess Body Weight Loss (%EBWL) or BMI will be compared with a tested Fishers Exact Test. Estimates and 95% confidence intervals will also be computed for the difference in rate of weight loss between varying stimulation levels.

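### The planning inputs in section 8.2 do not yield 75 per group at 80% power for continuous %TBWL under a standard fixed-design calculation, and the basis of 75 is not documented

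*Combined protocol and SAP*

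**What the plan says.** Section 8.2 sets out its planning inputs:

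- Control mean: "The sample size modeling assumes an average of 3.5% TBWL in Control subjects using diet and exercise alone".
- Treatment mean: 7.5% TBWL, taken from preliminary dermatomal TENS data.
- Spread: "The variance of the responses in the study (i.e. Standard Deviation) was modeled at + 5% TBWL".
- Dropout and power: "The model assumes a 30% drop out rate across groups and an 80% powered endpoint", under an adaptive spending approach with interim looks at cohorts of at least 25 per group.

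It then concludes: "This modeling provides an estimate of 75 subjects per group, for a total study size of 150 subjects". The Protocol Summary repeats this as "The primary endpoint is powered at a final enrollment of 75 subjects per group, for a total of 150 subjects", so 75 is an enrolled number.

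On the interims, section 8.2 says "The alpha penalty will be minimized per interim", because the looks are meant to project sample size and futility rather than test the primary hypothesis. It gives no alpha, sidedness, test, number of looks, spending function or simulation result. Further subjects may be added if the interim model projects too little power, and the summary allows up to 300.

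Section 6.1.2 defines a continuous endpoint: "The primary effectiveness endpoint is the percent reduction in total body weight loss (%TBWL"), as a percentage of initial weight. Section 8.1.3 instead frames weight loss as a probability and says the results "will be compared with a tested Fishers Exact Test". Sections 8.3 and 8.4 carry the last value forward in a modified intent-to-treat (mITT) population.

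**The concern.** A difference of 4 points with an SD of 5 is a standardised effect of 0.8. That normally needs about 25 per group for 80% power, and allowing for 30% loss still leaves fewer than 40. The plan's figure is about twice that.

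The gap matters for two reasons. First, the stated power for the primary endpoint is a figure that others rely on, and it does not follow from the inputs printed beside it. A reader cannot tell whether 75 was sized for 4 points, for about 2.8 points, for a larger SD or for a responder endpoint. Second, the plan lets an interim model add subjects when the primary endpoint looks underpowered. That judgement needs a known effect, SD, alpha and power target. A benchmark of 4 points with SD 5 differs materially from one of 2.8 points with SD 5, or of 4 points with SD 7.2.

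**Working it through.** **Inputs.** From section 8.2: difference 7.5 − 3.5 = 4 points, SD 5, dropout 30%, power 80%. From section 8.2 and the summary: 75 enrolled per group, equal allocation. Assumed, because the plan does not say: two-sided alpha 0.05 (suggested only by the 95% two-sided intervals in section 8) and a two-sample t-test.

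**Trying to reproduce 75.** The normal approximation is n = 2 × [(1.96 + 0.842) × SD / difference]² = 2 × (2.802 × 5/4)² = 24.5, so 25 per group. The exact noncentral t gives 79.1% power at n = 25 and 80.7% at n = 26, so 26 evaluable are needed. Allowing for dropout, 26 / 0.7 = 37.1, so 38 enrolled. With a one-sided 0.05 test, 21 evaluable are needed and 21 / 0.7 = 30 enrolled. Neither is 75.

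**Does an interim alpha penalty close the gap?** The table uses 80% power, 4 points, SD 5 and dropouts lost. Three looks are assumed from cohorts of 25 (75 / 25 = 3).

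| Two-sided alpha | Evaluable per group | Enrolled per group | Power with 52 evaluable |
|---|---|---|---|
| 0.05 | 26 | 38 | 98.1% |
| 0.025 | 31 | 45 | 96.3% |
| 0.0221 (Pocock, three looks) | 32 | 46 | 95.9% |
| 0.0167 (Bonferroni, three looks) | 35 | 50 | 94.8% |
| 0.005 | 44 | 63 | 88.4% |
| 0.0017 | 52 | 75 | 80.0% |

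Reaching 75 this way needs an alpha near 0.0017, while the plan says the penalty is to be kept small.

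**What 75 enrolled gives if dropouts are lost.** 75 × 0.7 = 52.5, taken as 52 evaluable. At two-sided 0.05, power is 98.1% for 4 points. Power is 80% for a difference of 2.77 points with SD 5, or for 4 points if the SD is 7.2.

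**What 75 gives under mITT with carry-forward.** All 75 are analysed. If dropouts dilute nothing, power for 4 points is 99.8%. If dropouts contribute no mean change, the difference becomes 4 × 0.7 = 2.8 points. The SD then depends on how dropouts vary. If they vary with the same SD of 5, the mixture variances are 25 + 0.21 × 7.5² = 36.8 for treatment and 25 + 0.21 × 3.5² = 27.6 for control (0.21 = 0.7 × 0.3). They average 32.2, an SD of about 5.67.

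| 75 analysed, difference 2.8 | Alpha 0.05 | Alpha 0.0221 |
|---|---|---|
| SD 5 | 92.6% | 87% |
| SD about 5.67 | 85% | 76% |

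**Routes that land at or near 75.** Each needs a choice the plan does not state.

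- Dilute to 2.8 points and also divide by 0.7: 52, then 52 / 0.7 = 74.3, so 75. This counts dropout twice.
- Use an SD of 5 × √2 = 7.07: 51, then 51 / 0.7 = 72.9, so 73.
- Dilute to 2.8 points with SD 5.67 and all analysed: 66 at alpha 0.05, 73 at 0.035, 76 at 0.03.
- Use Fisher's exact test on an assumed 5% responder cut. Under normality the proportions are Φ(0.5) = 0.691 and Φ(−0.3) = 0.382. This needs 68 enrolled at alpha 0.05, 73 at 0.03 and 78 at 0.025.

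**The case against.** The strongest reply is that section 8.2 describes an adaptive model, not a fixed-design t-test, and names no t-test for efficacy. Its primary population keeps dropouts by carry-forward, and section 8.1.3 names Fisher's test. Combining one dilution for dropout, a wider mixture SD and a modest alpha penalty brings the requirement to 73–76 without an extreme alpha and without counting dropout twice. A responder test with an alpha penalty also comes close.

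Much of this stands. A reader might infer that 75 with 80% power is impossible under any conventional alpha, or that true power must exceed about 93%. The documents do not support either inference. Carry-forward and an alpha penalty can apply together, and with SD 5.67 and alpha 0.0221 the power at 75 is 76%. For the same reason, a blanket assurance that the main comparison has power to spare is not supported. Nor do the documents show that dropout was counted twice, since several routes arrive near the same number.

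The reply does not make 75 follow from what is written. Every such route supplies a dropout pattern, an alpha, an SD or an endpoint that section 8.2 omits. A simulation could justify a number above the fixed-design one, but none is reported.

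**Conclusion.** The point holds for the continuous primary endpoint under a standard fixed-design calculation: the stated inputs give 38 enrolled per group, not 75, at 80% power. This assumes a two-sided 0.05 t-test with dropouts lost. On that basis the pairing of 75 with 80% should be about 98%, or about 95–96% at three-look Bonferroni or Pocock alphas. Under the carry-forward analysis no single power figure can be given, because dropout behaviour and alpha are unstated.

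Confidence is high that 75 cannot be reproduced from the printed inputs, and low about where it came from. A reader might also infer that the trial is oversized and could be cut to 38 per group. That does not follow: 38 rests on the completer assumption, and under diluted carry-forward the larger number may be needed. This should be corrected, but it does not invalidate the design.

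**What to change.** Keep enrolment at 75 per group and correct section 8.2 and the Protocol Summary in one of two ways.

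1. If 4 points and SD 5 are the real basis, restate the power and label the test, alpha and completer basis as assumptions. For example: with 52 evaluable per group after 30% dropout, SD 5% and an assumed two-sided 0.05 t-test, power is about 98% for 4 points and 80% for about 2.8 points. Add the corresponding figure for the mITT carry-forward analysis, with its assumed dropout behaviour and final alpha.
2. If 75 came from something else, such as a diluted effect, a larger SD, a spending rule, a simulation or a responder analysis, state the effect, SD, alpha, endpoint and dropout handling. Then reconcile that basis with the continuous endpoint in section 6.1.2 and the test named in section 8.1.3.

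In either case, use the same inputs and power target when the interim model judges whether the primary endpoint is underpowered. The cost is revised text and a short calculation, with no change to enrolment or procedures.

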#### 8.3 RETENTION AND HANDLING OF MISSING DATA

Every effort will be made to collect all data at each time point in the study. The PI and the Clinical Data Monitor will minimize the amount of missing data by appropriate management of the prospective clinical trial, proper screening of subjects, and training of clinicians. If a subject misses a dietary entry into either the paper or electronic diary, a look back entry for that value is allowed provide for the week preceding the event. Outside this window, data will be considered missing. All partial data available for subjects who drop out during the course of the study will be included.

For missing data imputation, the last value carried forward method will be utilized. To assess the potential effect of missing data on the primary effectiveness endpoint, the following sensitivity analyses will be performed to impute missing values.

Sensitivity Analyses: First, the primary effectiveness endpoint will be assessed with all missing data points imputed as failures for both groups. Second, the primary efficacy endpoint will be assessed with all missing data points imputed as successes for both groups.

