#### 5.1 Dosing Schedule

All Treatment Subjects will be trained in rotation of the patch electrodes every 24h such that it is applied to varying locations on the T6/T7 dermatome. Each active therapy subject will receive up to 30 mA sustained current of stimulation (up to 40mA peak) for 30 minutes after each of three meals per day (delivered within 1-hour post prandially). Based on tolerance of the therapy, a subject may decrease his or her dose by dropping one of the 3 post prandial sessions after receiving approval from a clinical coordinator and/or PI. Subjects who do not experience sufficient appetite suppression may add up to three 15-minute pre-prandial rescue sessions delivered within 2 hours before each meal after receiving approval from a clinical coordinator and/or PI. The nominal stimulation dose per day for any subject will thus be 2400 mA (60 minutes at 40 mA) while the maximum dose for any given subject will be 5400 mA (135 minutes at 40 mA).

During the therapy period, Treatment Subjects will undergo initial assessments to ensure they are familiar with the device, the daily electronic diary, weekly paper diary, and the 1200 calorie diet. All subjects (Treatment and Control) will be required to undergo follow-up assessments at least once per every 4 weeks during the study. Up to two additional unscheduled visits per subject will be permitted during the study. PI will oversee any adjustments to treatment dosing or stimulation parameters.

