#### 5.2 DATA COLLECTION:

All subjects will be asked to keep a VAS paper diary (hunger, appetite, well-being) in which they will record such values weekly. Subjects will record their diary variables. For treatment subjects, any adjustments to stimulation session schedule will be recorded within the electronic diary and by clinical coordinators.

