#### 6.1.3 Secondary Effectiveness Endpoints:

- Number of subjects reporting >5% total body weight loss at the end of Therapy as compared to Baseline between Treatment and Control
- Percent change in appetite scores at the end of Therapy Period compared to Baseline between Treatment and Control.
- Blood pressure, blood lipids, ALT and HbA1c at the end of Therapy Period as compared to Baseline between Treatment and Control groups.
- % changes in BMI at the end of Therapy Period compared to Baseline between Treatment and Control groups

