#### 6.2 ENDPOINT DEFINITIONS & RECORDING METHODS

Endpoint data in hunger, appetite, and dietary compliance are obtained from subject reported assessments (Appendix 4, 5). That is, the measurement of success is based on the subject's report of the parameter using validated tools where available.

Primary source data will be paper based, with each subject receiving diary worksheets to record responses. Treatment subjects will also be assigned an Android Smart Phone onto which has been loaded a copy of custom dietary application (Appendix 5). Subjects will be trained on the use of these tools and assessed for accurate use prior to taking them home. To ensure data privacy, the network interface card (i.e. SIM card) for the phone will be removed such that data can only be downloaded *via* a direct USB link.

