# 18.5 APPENDIX 5: VAS AND DAILY DIARY APPLICATION

# Recommended primary scales for self-reported appetite in healthy adultsa

Scale Question		Anchors					
		Low	High				
Hunger	How hungry are you?	Not at all	Extremely As hungry as I have ever felt				
Fullness	How full are you?	Not at all	Extremely As full as I have ever felt				
Satiety	How satiated are you?	Not all	Extremely				
Desire	How strong is your desire to eat?	Very weak Extremely low	Very strong Extremely high				
Prospective consumption (Quantity)	How much do you think you could (or would want to) eat right now?	Nothing at all	A very large amount				

<sup>aLine scales 100-150 mm (paper) or appropriate length for electronic capture systems are to be used for each of these questions.

**44** | Page E L I R A - 1

E LIRA	petite Assessment Diary Protocol: CD-004	
THERAPEUTICS Subject Initials:	Subject Number:	
Directions: Answer each question abut how you ar	re feeling by drawing a mark (   ) through the horizontal line of each question.	
Please complete prior to mealtime. TIME:	_ DAM DATE:	
Table 1 Please indicate below your level of nausea:	Table 2 How Satisfied do you feel?  I am not hungry at all	I have never been more hungry
None Worst Ever  Please indicate below your level of fullness:	I am How full do you feel?  completely empty	I cannot eat another bite
None Worst Ever  Please indicate below your level of bloating:	How hungry do you feel?  Not full	
None Worst Ever	at all  How much do you think you can eat?  Nothing	Totally full
Please indicate below your level of abdominal pain:	Table 3 Would you like to eat something sweet?	A lot
None Worst Ever	Yes, very much	No, not at all
To be completed by study staff:	Would you like to eat something salty?  Yes, very much	No, not at all
Scoring:	Would you like to eat something savory?	
Table One: 1 2 3 4 Table Two: 1 2 3 4	Yes, very much  Would you like to eat something fatty?	No, not at all
Table Three: 1 2 3 4	Yes, very much	No, not at all

**45** | Page E L I R A - 1

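### As worded, the one-week look-back in Section 8.3 admits recalled ratings into the momentary appetite VAS diary, a possible source for an open-label secondary endpoint

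*Combined protocol and SAP*

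**What the plan says.** The rule in Section 8.3 begins "If a subject misses a dietary entry into either the paper or electronic diary" and continues "a look back entry for that value is allowed provide for the week preceding the event". Outside that window the value is missing, and the section then imputes by last value carried forward. Its two sensitivity analyses concern the primary effectiveness endpoint only.

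Section 5.2 describes the paper diary: "All subjects will be asked to keep a VAS paper diary (hunger, appetite, well-being) in which they will record such values weekly". The Protocol Summary describes paper diaries for appetite and symptoms, and Section 9.8 has them kept from screening to the end of the study. The form in Appendix 5 consists of line ratings of symptoms, appetite and cravings in the present tense. It carries the instruction "Please complete prior to mealtime" and blank spaces for time and date. It names no meal and no weekday. The recommended scales in the same appendix are also momentary, for example "How much do you think you could (or would want to) eat right now".

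Section 6.1.3 lists as a secondary endpoint "Percent change in appetite scores at the end of Therapy Period compared to Baseline between Treatment and Control". Section 6.2 states "Endpoint data in hunger, appetite, and dietary compliance are obtained from subject reported assessments (Appendix 4, 5"; those appendices are the TFEQ-R18V2 and the VAS diary. Section 2.1 has appetite change measured weekly by VAS and also assessed by TFEQ-R18V2. Section 8.1.2 takes the TFEQ as the appetite score when correlating with dose. Section 5.3 makes the study open label.

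**The concern.** A rating of present hunger before a meal cannot be made days afterwards. A later mark is a recollection, and the form has no recall version. Subjects know whether they wore the device, so a score recalled during treatment can be coloured by what they expect the device to have done. A value that would have been visibly missing then becomes an observed score that may depend on arm, and nothing in the plan allows it to be separated out later.

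The unfixed meal adds to this. Stimulation is given "for 30 minutes after each of three meals per day (delivered within 1-hour post prandially", so a rating before breakfast follows an overnight gap, while one before a later meal may follow a session by a few hours. Section 5.1 also permits added sessions within 2 hours before meals for subjects with insufficient appetite suppression. Time since stimulation, like ordinary time-of-day hunger, therefore varies with the meal the subject chooses. With one form a week, a single recalled mark is the whole of that week's value.

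**Working it through.** There is no plan figure to reproduce. The check sets the sections side by side and then illustrates the size under assumptions.

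**1. What the rule reaches.** Section 8.3 speaks of a dietary entry, which could mean food or calories only. But it names the paper diary, and the Appendix 5 paper form has no calorie, food or weight field. Calories and weight are captured in the electronic diary (Section 9.11), which only treated subjects have. Including VAS ratings is the natural reading, though not the only one.

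**2. Whether late entries can be identified.** The form has a time and date box. No section says whether it should show the meal being rated or the moment of marking. No section requires look-back entries to be flagged, limited in number, or excluded in a sensitivity analysis.

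**3. Whether the endpoint is reached.** Sections 2.1 and 6.2 make the VAS a source for appetite data. Section 8.1.2 uses the TFEQ, which is administered at Visits 1 to 5 and which look-back does not touch. Exposure is therefore conditional on the instrument.

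**4. Which errors can differ by arm.** The screening diary is dispensed at Visit 0 and collected at Visit 1, the randomisation visit. A baseline mark recalled before allocation adds noise, not arm bias. Ordinary variation from the unfixed meal also mainly adds noise, and it affects on-time entries too. Recalled scores during treatment can differ by arm. Treated subjects alone also record hunger on a phone (Section 9.11), so their aids to recall differ.

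**5. Illustrative size.** Let *f* be the share of end-of-therapy scores recalled, equal in both arms, and *b* the between-arm difference in mean recall error, in SD units. Both are assumed. For *n* per arm, with an unadjusted two-sided 5% z-test:

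- Bias in the arm difference = *f* × *b*.
- Shift of the test statistic: *m* = *f b* / √(2/*n*).
- Type I error = 1 − Φ(1.96 − *m*) + Φ(−1.96 − *m*).

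Take *n* = 75 (Section 8.2), and 52 after the plan's 30% dropout (75 × 0.70 = 52.5).

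| *f* | *b* (SD) | Bias (SD) | Type I error, *n* = 75 | Type I error, *n* = 52 |
|---|---|---|---|---|
| 0.10 | 0.25 | 0.025 | 5.27% | 5.19% |
| 0.10 | 0.50 | 0.050 | 6.08% | 5.75% |
| 0.20 | 0.25 | 0.050 | 6.08% | 5.75% |
| 0.20 | 0.50 | 0.100 | 9.39% | 8.03% |
| 0.30 | 0.25 | 0.075 | 7.45% | 6.69% |
| 0.30 | 0.50 | 0.150 | 15.08% | 11.92% |

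For the last row at 75 per arm: *m* = 0.15 / √(2/75) = 0.15 / 0.1633 = 0.919, giving 15.08%. If recall error is equal in the two arms, *b* = 0 and the difference is unbiased.

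In millimetres, under separate assumptions on a 100 mm line, 0.10 × 10 mm = 1 mm and 0.30 × 20 mm = 6 mm. The documents give no VAS SD, so these cannot be converted to SD units.

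**The case against.** A reader might infer that for the paper diary the rule can only mean VAS scores. The documents do not go that far. Section 6.2 lists dietary compliance apart from hunger and appetite and refers to diary worksheets in the plural, so the Appendix 5 page need not be the whole paper diary. The wording is ambiguous. What stands is that a site following it literally could accept recalled VAS marks.

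A reader might also infer that recalled scores necessarily enter the appetite endpoint. Section 8.1.2 points to the TFEQ, and if that alone defines the endpoint, look-back does not reach it. Sections 2.1 and 6.2 do not support so narrow a definition. The instrument is simply unsettled.

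Declaring every late form missing would, under the same section, pass it to last value carried forward. That replaces a recalled rating with an earlier week's rating, which may itself be biased by arm. This objection stands in full, and the remedy has to deal with it.

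With no weekday or meal fixed, a late subject could complete the form before the next meal as a valid present-state rating. That is true, and the remedy can use it. But the present wording does not separate such a rating from one reconstructed for an earlier meal.

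The plan has safeguards: training and a check of accurate use (Section 6.2), diary review at therapy visits, and an audit trail for diary changes (Section 15). They help, but none identifies a paper rating made from memory. On-time ratings are also unblinded, so the extra bias due to recall is unknown. A fixed meal samples only one interval since stimulation, and the time box permits some adjustment; these points temper the case for fixing the meal but leave the look-back problem untouched.

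**Conclusion.** The point holds in limited form. As worded, Section 8.3 admits recalled ratings into a scale built for present-state ratings, in an open-label trial, with no flag and no sensitivity analysis. At stake is the secondary appetite endpoint, to the extent that it uses the VAS. Percent total body weight loss, based on weight obtained at clinic visits, is not affected.

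The possible arm-dependent error lies in scores recalled during treatment. That recalled baseline marks or the floating meal bias the comparison by arm is a stronger claim, which the visit order and randomisation do not support; they mainly add noise.

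The size cannot be derived from the documents. The type I error range of about 5.3% to 15.1% at 75 per arm (5.2% to 11.9% at 52) rests entirely on the assumed recall share and differential bias. It shows what could happen, not what will. The change is worth making because it is cheap and because unflagged recalled scores cannot be identified afterwards.

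**What to change.** - **Section 8.3, look-back:** limit it to factual entries (calories, weight), and say that VAS ratings are not to be reconstructed from memory.
- **Appendix 5 form:** print one fixed meal and one weekday, the same in both arms. Allow a short stated window, for example until the next day, in which a late form is completed as a new present-state rating before the same meal. Record the actual completion date and time, and flag late forms.
- **Section 8.3, missing VAS:** treat forms outside that window as missing and exempt them from last value carried forward. Analyse the available weekly scores with a repeated-measures model and take the end-of-therapy arm contrast from it. Add a sensitivity analysis that excludes flagged late entries.
- **Sections 6.1.3 and 8.1.2:** state which instrument, VAS or TFEQ-R18V2, defines the appetite score, and reconcile this with Sections 2.1 and 6.2.

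The cost is wording in the protocol and on the form, somewhat more missing weekly VAS values, and a little more analysis work. The repeated-measures model assumes that missingness is explained by the observed data, and the plan should say so.

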#### 8.4 SUBJECT POPULATION FOR SAFETY AND EFFECTIVENESS ANALYSIS

Safety analyses will be conducted an Intent to Treat (ITT) basis (i.e. all subjects who were enrolled). Primary and Secondary effectiveness analyses will be performed on a modified intent-to-treat basis (MITT; i.e. all subjects who initiated therapy, defined as subjects who initiated their first Treatment Period Visit) as will all per subject effectiveness analyses (e.g. responder analyses). Primary and Secondary endpoints (e.g. weight loss, appetite) will also be conducted on a completer, or per protocol basis (defined as those subjects that completed all visits in the study).

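### Section 8.3 carries the last weight forward for an assumed 30% dropout, which dilutes the planned effect, and its failure/success sensitivity analyses cannot be run on the continuous primary endpoint

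*Combined protocol and SAP*

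**What the plan says.** - **Dropout.** Section 8.2: "The model assumes a 30% drop out rate across groups". It gives no figure by arm.
- **Base method.** Section 8.3: "For missing data imputation, the last value carried forward method will be utilized". It adds: "All partial data available for subjects who drop out during the course of the study will be included".
- **Sensitivity analyses.** Section 8.3, first analysis: "the primary effectiveness endpoint will be assessed with all missing data points imputed as failures for both groups". The second imputes all missing values as successes in both groups.
- **Endpoint.** Section 6.1.2 defines the primary endpoint as percent change in body weight, with no threshold. Section 8.1.3 writes the hypotheses in terms that "are the probabilities of weight loss (% TBWL, %EBWL) in treatment versus control respectively", and says the estimates "will be compared with a tested Fishers Exact Test"; it gives no threshold either. The only threshold, more than 5% loss, belongs to a secondary endpoint in 6.1.3, and 8.3 does not refer to it.
- **Populations.** Section 8.4 reserves ITT for safety. Effectiveness uses a modified ITT set, "all subjects who initiated therapy, defined as subjects who initiated their first Treatment Period Visit", and "will also be conducted on a completer, or per protocol basis".
- **Other imputation wording.** The Protocol Summary (Subject Population / Sample Size, and Statistical Analysis) and the opening of section 8 allow multiple imputation in the Bayesian efficacy analyses. The first ties it to the interims; the other two do not.
- **Weights available.** Appendix 6 schedules weight at every visit, and its footnote 7 calls for all end-of-study procedures at an early-termination visit.

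**The concern.** If weight is still falling over the 12 weeks, a carried-forward weight freezes a dropout at a partial loss. With nearly a third of subjects assumed to leave, this alters the estimate even when both arms lose subjects alike. The trial is open label (5.3): controls know they have diet alone, and only device subjects must tolerate stimulation. A difference between arms in the rate or timing of leaving is therefore plausible, and it would bias the primary comparison.

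Sensitivity analyses should show how far the result depends on the missing data. Here the planned pair has no meaning for a continuous endpoint. The plan also leaves open which imputation method governs the efficacy result and which subjects are in it.

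**Working it through.** **The plan's own figure.** A two-sided 5% comparison of means with difference 4.0, SD 5 and 80% power needs 2 × (1.96 + 0.84)² × 25/16 ≈ 24.5, so 25 per arm; 25/0.7 gives 36 with 30% dropout. The stated 75 does not follow from these inputs, but the spending model is not specified and nothing below depends on how 75 was reached.

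**Inputs.** From 8.2: 7.5% and 3.5% mean loss, SD 5, 30% dropout, 75 per arm. Assumed: linear loss over 12 weeks; last weight at week 1, 4 or 8; SD unchanged by imputation; two-sided 5% comparison of means (8.2 states no alpha).

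**Formula.** With mean loss m, dropout d and carried fraction f = (last week)/12, the carried-forward arm mean is m × [(1 − d) + d × f]. SE = 5 × √(2/75) = 0.816. Positive differences favour the device. Splits are device/control.

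| Case | Week 1 (f = 0.083) | Week 4 (f = 0.333) | Week 8 (f = 0.667) |
|---|---|---|---|
| Effect 4.0, equal 30%: 4.0 × (0.7 + 0.3f) | 2.90 | 3.20 | 3.60 |
| Power for that difference | 94% | 97% | 99% |
| No effect, 25/35: 3.5 × 0.10 × (1 − f) | +0.32 | +0.23 | +0.12 |
| No effect, 20/40: 3.5 × 0.20 × (1 − f) | +0.64 | +0.47 | +0.23 |
| Effect 4.0, 20/40 | 3.91 | 3.93 | 3.97 |
| Effect 4.0, 40/20 | 1.89 | 2.47 | 3.23 |

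With no effect and equal rate and timing, the two arm means are identical and the bias is zero. Reversing a split flips the sign. Timing alone can also bias the result: with no effect, 30% leaving in each arm and last weights at week 8 (device) and week 4 (control), the bias is 3.5 × 0.3 × (0.667 − 0.333) = +0.35; reversed, −0.35.

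These figures fall as f rises, which is what early-termination weights or front-loaded loss would do. At an assumed f = 0.9, the equal-dropout effect is 4.0 × (0.7 + 0.27) = 3.88 and the 20/40 null bias is 3.5 × 0.20 × 0.10 = 0.07.

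**Alternatives compared by simulation** (75 per arm, poor losers leaving more often on observed weights). No effect, 20/40: carrying forward +0.49, completers −0.49, by-arm multiple imputation +0.01. Effect 4.0, equal 30%: 3.25, 4.00 and 4.00. Completers and carrying forward can thus err in opposite directions, so the completer analysis does not settle the matter.

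**Sensitivity pair.** It needs each missing subject labelled a success or a failure. Sections 6.1.2, 8.1.3 and 8.3 give no cut-off for the label, so the analysis is undefined for the primary endpoint.

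**Modified ITT.** If the trigger is Visit 1, where section 9 places the start of therapy, the set is nearly all randomised and the gap is about nil. If it is Visit 2, the first therapy-phase visit, early leavers are lost. If 5% to 15% of device subjects (no source) left before then and would have lost 3.5%, modified ITT would show 4.0, against (1 − x) × 7.5 + x × 3.5 − 3.5 = 3.8 to 3.4 for all randomised.

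**The case against.** The strongest reply is that the documents' only dropout figure is 30% across groups. On that input, with equal timing, carrying forward produces no false positives and only makes the trial conservative, with power still above the planned 80%. That stands, and it limits how serious the point is.

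A reader might infer that the plan inflates the false-positive rate. In a two-sided comparison of means, the 20/40 cases above would give 5.9% to 12.3%. The documents do not support this as a finding: no arm-specific dropout is given, and 8.1.3 names Fisher's exact test with a one-sided alternative. Nor is carrying forward conservative only when dropout matches between arms: the 40/20 row shows a true 4.0 shrinking to between 1.89 and 3.23.

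Two other strong readings also fail. Section 8.4 does not clearly exclude early leavers, because the Visit 1 reading is open. Nor is it a serious omission that no analysis counts treatment dropouts as failures and control dropouts as successes. Borrowing the 5% rule (69.1% against 38.2% responders under the normal model), that bound reverses a true benefit once equal dropout passes about 23.6%, so at 30% it is nearly uninformative. With the same rule the planned pair does give some warning when dropout is unequal: with no effect and 20/40, it yields +7.6 and −12.4 percentage points. But 8.3 does not adopt that rule.

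Finally, multiple imputation is not uniformly better. In the simulation, when leaving depends on the unseen week-12 loss (no effect, 20/40), it gave −0.55 and carrying forward +0.12. This stands, and is why the sensitivity analyses matter.

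**Conclusion.** The point holds as a low-cost improvement to the analysis plan. At the plan's own 30% dropout, carrying forward costs about 0.4 to 1.1 points of a 4.0-point effect (4.0 − 3.6 and 4.0 − 2.9), assuming linear loss and equal rate and timing. Bias between the arms is possible in either direction, but its size is hypothetical, since it rests on assumed splits and last-visit weeks and shrinks if early-termination weights are obtained.

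Three parts need no numerical assumption: the sensitivity pair is undefined for the primary endpoint, the modified ITT trigger visit is not identified, and the multiple-imputation wording is not reconciled with 8.3. The documents do not show that the trial's error rate is inflated or that early leavers are excluded.

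**What to change.** (a) In 8.3 and 8.4, make the primary effectiveness analysis all randomised subjects as assigned. Estimate week-12 percent weight change by multiple imputation within arm from scheduled and early-termination weights, or by an equivalent longitudinal model, adjusted for baseline weight. Drop last value carried forward as the primary method. State that the analysis assumes leaving depends on observed weights.

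(b) For the continuous endpoint, replace the failure/success pair with control-based imputation and a tipping-point analysis that shifts each arm separately. For the >5% endpoint, count missing as non-responder; treatment-failure/control-success is optional, as an extreme bound.

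(c) Keep modified ITT, with its trigger visit defined for both arms, and completers as supportive analyses. On the Visit 2 reading, by-arm imputation alone would still give about 4.0; the control-based analysis is what reflects early leavers.

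(d) Reconcile the multiple-imputation wording in the Protocol Summary and section 8 with 8.3.

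**Cost.** SAP wording and modest extra analysis; no new data. The estimate may move either way: removing carry-forward may raise it from 2.9–3.6 towards 4.0, while imputing all 30% of device dropouts as controls gives 0.7 × 4.0 = 2.8 points, with about 93% power at 75 per arm.
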